4. REGISTRATION PROCEDURES

4.1. General Guidelines for DF/HCC and DF/PCC Institutions

Eligible patients will be entered on study centrally through the Quality Assurance Office for Clinical Trials (QACT) at the Dana-Farber Cancer Institute at the time of study enrollment. Completed QACT eligibility checklists and signed consent forms should be faxed to the QACT at [contact] prior to subjects starting protocol treatment. The checklist will be reviewed at that time and the subject registered by the QACT Protocol Registrars [contact]).

Following registration, patients should begin protocol treatment within 5 days. Other issues that would cause treatment delays should be discussed with the Principal Investigator. If a patient does not receive protocol therapy following registration, the patient's registration on the study may be canceled. The Study Coordinator should be notified of cancellations as soon as possible.

Except in very unusual circumstances, each participating institution will order DCTD-supplied agents directly from CTEP. Agents may be ordered by a participating site only after initial IRB approval for the site has been forwarded by the Coordinating Center to the CTEP PIO ([contact]) except for Group studies.

4.2. Registration Process for DF/HCC and DF/PCC Institutions

The QACT registration staff is accessible on Monday through Friday, from 8:00 AM to 5:00 PM Eastern Standard Time. In emergency situations when a participant must begin treatment during off-hours or holidays, call the QACT registration line at [contact] and follow the instructions for registering participants after hours.

Randomization can only be done between normal QACT business hours, 8:00 AM to 5:00 PM Eastern Standard Time.

The registration procedures are as follows:

1. Obtain written informed consent from the participant prior to the performance of any study related procedures or assessments.
2. Complete the protocol-specific eligibility checklist using the eligibility assessment documented in the participant's medical/research record. **To be eligible for registration to the study, the participant must meet each inclusion and exclusion criteria listed on the eligibility checklist.**

Reminder: Confirm eligibility for ancillary studies at the same time as eligibility for the treatment study. Registration to both treatment and ancillary studies will not be completed if eligibility requirements are not met for all studies.

3. Fax the eligibility checklist(s) and all pages of the consent form(s) to the QACT at [contact].

Exception: DF/PCC Affiliate sites must fax the entire signed consent form including HIPAA Privacy Authorization and the eligibility checklist to the Network Affiliate Office. The Network Affiliate Office will register the participant with the QACT.

4. The QACT Registrar will (a) validate eligibility, (b) register the participant on the study, and (c) randomize the participant when applicable.
5. The QACT Registrar will send an email confirmation of the registration and/or randomization to the person initiating the registration immediately following the registration and/or randomization.

4.3. Registration Process for non DF/HCC Institutions

Registration for non-DF/HCC Institutions will be as detailed in the Data Safety Monitoring Plan (DSMP). Please refer to the DSMP, Appendix G, Section 5.7 for specific procedures.

5. TREATMENT PLAN

Treatment will be administered on an outpatient basis. Expected toxicities and potential risks as well as dose modifications for cediranib and olaparib are described in Section 6 (Expected Toxicities and Dosing Delays/Dose Modifications). No investigational or commercial agents or therapies other than those described below may be administered with the intent to treat the participant's malignancy.

Phase I

Each cycle will be 28 days (4 weeks). For the Phase I component of this study, treatment cohorts will consist of 3 to 6 patients and the dose escalation schedule will be as follows. Participants enrolled to the Phase I portion of the study will continue treatment with olaparib capsule formulation.

	Dose Level	Cediranib	Olaparib (capsule)
	-1	15mg PO daily	100mg PO BID
Starting dose →	0	20mg PO daily	100mg PO BID
	1	20mg PO daily	200mg PO BID
	2	30mg PO daily	200mg PO BID
	3	30mg PO daily	400mg PO BID

Phase I-T

For the Phase I-T component of this study, treatment cohorts will consist of 3 to 6 patients. Two separate cohorts of dose escalation will be accrued, one with a dosing of cediranib at 30mg daily (Phase I-TA) and a second at cediranib dosing of 20mg daily (Phase I-TB). The two Phase I-T

dose escalation schemes will enroll in parallel. Participants enrolled to the Phase I-T portion of the study will receive treatment with the olaparib tablet formulation. The dose escalation schedule for the two cohorts will be per the following tables. If the cohort of patients enrolled in a given dose level completes the DLT assessment window without experiencing a DLT in the first three patients or with 1 or fewer DLTs in six patients, the next higher dose level may be assessed.

Phase 1-TA Dose Escalation: Cediranib 30mg

	Dose Level	Cediranib	Olaparib (tablet)
	-1-TA	30mg PO daily	100mg PO BID
Starting dose →	0-TA	30mg PO daily	150mg PO BID
	1-TA	30mg PO daily	200mg PO BID
	2-TA	30mg PO daily	250mg PO BID
	3-TA	30mg PO daily	300mg PO BID

Phase 1-TB Dose Escalation: Cediranib 20mg

	Dose Level	Cediranib	Olaparib (tablet)
	-1-TB	20mg PO daily	150mg PO BID
Starting dose →	0-TB	20mg PO daily	200mg PO BID
	1-TB	20mg PO daily	250mg PO BID
	2-TB	20mg PO daily	300mg PO BID

Toxicity assessments will be done using NCI Common Terminology Criteria for Adverse Events (CTCAE v4.0). CTCAE v4.0 is identified and located on the CTEP website at (http://ctep.cancer.gov/protocolDevelopment/electronic_applications/ctc.htm). Dose escalation to the next dose level will occur when the preceding cohort reaches the end of Cycle 1. Patients who do not complete both treatments in cycle 1 for reasons other than cediranib or olaparib toxicity will be replaced. Toxicity data for each cohort will be reviewed prior to dose escalation. Intra-patient dose escalation will be allowed at the discretion of the investigator and overall trial PI for patients following their completion of Cycle 2 if the following criteria are met: the patient had no > grade 1 toxicities secondary to study treatment except for grade 2 or 3 HTN or nausea no greater than grade 1 after treatment with concurrent medications, the subsequent dose cohort has completed Cycle 1, and evaluation of DLTs has been completed for the subsequent dose cohort and the dose was deemed to be safe due to ≤ grade 2 toxicities. Dose escalation will occur for both cediranib and olaparib according to the dose escalation schema. Patients can be dose-escalated multiple times as long as they continue to meet criteria and do not exceed the final protocol-specified dose level (dose Level 3). All intra-patient dose escalations must be discussed and approved by the overall trial PI. If treatment-related toxicities related to one of the study drugs restricts further escalation of that drug, a modification to the dose escalation schema may be considered.

Phase I-T PK expansion

Once the MTD has been established during the Phase 1-T, two PK expansion cohorts of 6 evaluable patients each will be enrolled for pharmacokinetic studies. Participants in this expansion will receive a one week of either single-agent cediranib (Cohort 1-T PKced) or single-

agent olaparib (tablet formulation; Cohort 1-T PKolap) prior to starting cycle 1 of combination cediranib and olaparib (tablet formulation). Full details of the PK evaluation schedule are outlined in Section 8.14. Participants must be able to continue on study drug without any dose holds through Cycle 1 Day 16 of treatment to be considered fully evaluable for PK studies.

Participants participating in the PK expansion cohorts will take their study drugs on the following schedule once combination dosing has started:

1. Cediranib tablet(s) in the morning on an empty stomach (at least 2 hours after eating)
2. Light meal ~1 hour after taking cediranib
3. Morning olaparib tablet(s) after light meal
4. Evening olaparib tablet(s) 12 hours after morning olaparib dose, taken after a light meal

Phase II

For the Phase 2 portion of this study, patients will be randomized in 1:1 ratio to one of the two following arms:

1. Olaparib 400mg BID (capsule)
2. Cediranib and olaparib at the RP2D (cediranib 30mg daily and olaparib 200mg BID (capsule)) derived from the Phase I portion of this study

Participants enrolled to the Phase II portion of the study will continue treatment with olaparib capsule formulation.

All patients must meet the eligibility criteria for the Phase II portion of the study, as outlined in Section 3. Patient randomization will be stratified based upon:

1. Prior receipt of anti-angiogenic therapy.
2. BRCA mutation status (carrier, non-carrier, unknown).

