5.2.2. Olaparib

Olaparib Capsules (Phase I and Phase II Participants)

Olaparib at the appropriate dose level will be given orally continuously twice daily on an empty stomach. The correct number of 50mg capsules comprising the appropriate dose should be taken at the same times each day with approximately 240 mL of water. Patients should take olaparib on an empty stomach either 1 hour before or 2 hours after meals. The olaparib capsules should be swallowed whole and not chewed, crushed, dissolved, or divided.

Olaparib will be dispensed at the start of each cycle. Patients will be provided with a pill diary (Appendix B), instructed in its use, and asked to bring it with them to each appointment.

If vomiting occurs shortly after the olaparib capsules are swallowed, the dose should only be replaced if all of the intact capsules can be seen and counted. Should any patient enrolled on the study miss a scheduled dose, the patient will be allowed to take the scheduled dose up to a maximum of 2 hours after that scheduled dose time. If greater than 2 hours after the scheduled dose time, the missed dose should not be taken, and the patient should take their allotted dose at the next scheduled time.

Olaparib Tablets (Phase I-T Participants)

Olaparib at the appropriate dose level will be given orally continuously twice daily on an empty stomach. The correct number of 25mg, 100mg, or 150mg tablets comprising the appropriate dose should be taken at the same times each day with approximately 240 mL of water. Patients should take olaparib on an empty stomach either 1 hour before or 2 hours after meals. The olaparib tablets should be swallowed whole and not chewed, crushed, dissolved, or divided.

Olaparib will be dispensed at the start of each cycle. Patients will be provided with a pill diary (Appendix B), instructed in its use, and asked to bring it with them to each appointment.

If vomiting occurs shortly after the olaparib tablets are swallowed, the dose should only be replaced if all of the intact tablets can be seen and counted. Should any patient enrolled on the study miss a scheduled dose, the patient will be allowed to take the scheduled dose up to a maximum of 2 hours after that scheduled dose time. If greater than 2 hours after the scheduled dose time, the missed dose should not be taken, and the patient should take their allotted dose at the next scheduled time.

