7.2.3. Route of Administration

Oral. Olaparib capsules or tablets should be taken either 1 hour before or 2 hours after meals.

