8.14. Pharmacokinetic (PK) studies

The steady-state plasma pharmacokinetics of cediranib and olaparib will be defined in a group of 12 patients in the safety expansion cohort treated with the recommended phase II doses of the combination, cediranib 30 mg QD and olaparib 200 mg BID, to assess whether or not the pharmacokinetic behavior of the two drugs is altered by their concurrent administration. Pharmacokinetic sampling will be performed during a single 24 h dosing interval after steady-state pharmacokinetic conditions for the repeated oral dosing schedules have been achieved when each agent is given alone (cycle 0) and again when given together in the same patient (cycle 1). In cycle 0, one group of six patients will receive single agent cediranib p.o. once daily for 7 days and the other group of six patients will receive single agent olaparib p.o. twice daily for 7 days. Pharmacokinetic samples will be collected on day 7 before and for 8 h after the dose is taken in the morning and before dosing on day 8. Combination therapy will begin on day 8 which is formally day 1 of cycle 1. Pharmacokinetic samples will again be collected before and for 8 hr after dosing on days 15-16 after the patients have received 14 days of combined therapy, as per the timepoints outlined below.

The sampling schedule has been devised to accommodate treatment on an outpatient basis. Patients will be instructed to take the doses of the two drugs as per outlined in the protocol at the same time every day during the pharmacokinetic study. Cediranib will be taken first thing in the morning on an empty stomach. One hour later, the patient may have a light meal, followed by the morning dose of olaparib. Dosing should be scheduled for times that will allow the patient to arrive at the clinic to obtain pharmacokinetic samples before dosing and to remain for an additional 8 hours after the morning dose of olaparib. The second daily dose of olaparib should be taken 12.0 ± 0.25 h after the morning dose. It is very important that the patient is aware that the morning doses of the two drugs on day 8 and day 16 must not be taken before arriving at the clinic and the 24.0 h pharmacokinetic sample has been collected. The first set of blood samples (6 mL) will be obtained during cycle 0 shortly before taking the day 7 dose of the single agent drug and at 0.5, 1.0, 2.0, 3.0, 4.0, 6.0, 8.0, and 24.0 h after dosing.

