Send complete sets of samples from one or more patients by next day delivery to the address listed below. Place the sample tubes in a zip lock plastic bag. Package samples in a seamless styrofoam container. Place the sample bag over at least 3-4 inches of dry ice on the bottom of the container and completely cover with an additional 3-4 inches or more of dry-ice. Seal the styrofoam container within a tight-fitting cardboard shipping box. Insert copies of the Pharmacokinetic Data Form for each set of samples into a separate zip-lock plastic bag placed on top of the styrofoam container before the external shipping box is sealed. Send the samples from Monday to Wednesday by overnight courier for delivery by 10 a.m. on the following day. Samples should not be shipped on a Thursday or Friday. Please provide notification of the sample shipment by e-mail to shipping to [contact] and [contact].

[name]
 Massachusetts General Hospital
 [name]
 Boston, MA 02114
 [contact]

The concentration of cediranib and olaparib in the plasma samples will be determined by the DF/HCC Cancer Pharmacology Core laboratory located on the main campus of the Massachusetts General Hospital (Boston, MA). An analytical method facilitating the concurrent determination of the two drugs based upon for both compounds based upon high performance liquid chromatography with tandem mass spectrometric detection has been developed. The analytical methods will be validated and applied to the analysis of study samples as recommended by the FDA Guidance for Industry: Bioanalytical Method Validation, May 2001 (<http://www.fda.gov/-downloads/Drugs/Guidances/ucm070107.pdf>).

Individual patient plasma concentration-time curves will be analyzed by noncompartmental methods using routines supplied in the WinNonlin Professional Version 5.0.1 software package (Pharsight Corp., Cary, NC). Pharmacokinetic parameters and variables will be calculated according to standard equations. Mean values of pharmacokinetic parameters will be statistically compared using the paired two-tailed t-test of the log-transformed data.

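### PK expansion, olaparib lead-in cohort: the protocol does not settle whether olaparib is taken fasted or fed in the single-agent week, so food may be confounded with cediranib in the paired comparison

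*Combined protocol and SAP*

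**What the plan says.** The design is in Section 8.14. Six patients take olaparib alone for 7 days (cycle 0) and then the combination. Olaparib is sampled on day 7 of cycle 0 and on day 15 of cycle 1, each with a 24-hour sample the next morning. The stated purpose is to learn whether giving the drugs together alters the pharmacokinetics of either. The analysis is: "Mean values of pharmacokinetic parameters will be statistically compared using the paired two-tailed t-test of the log-transformed data". Section 1.3.4 lists the PK profile of the combination as a Phase 1-T secondary objective.

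Five places bear on food and olaparib:

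- **Section 5, Phase I-T PK expansion.** The meal schedule is introduced by "Participants participating in the PK expansion cohorts will take their study drugs on the following schedule once combination dosing has started" and includes "Morning olaparib tablet(s) after light meal". For the PK evaluation it defers to another section: "Full details of the PK evaluation schedule are outlined in Section 8.14".
- **Section 5.2.2, tablets for Phase I-T.** Patients "should take olaparib on an empty stomach either 1 hour before or 2 hours after meals". There is no exception for the PK cohorts.
- **Section 7.2.3.** "Olaparib capsules or tablets should be taken either 1 hour before or 2 hours after meals". Again there is no exception.
- **Section 8.14.** Patients take "the doses of the two drugs as per outlined in the protocol at the same time every day during the pharmacokinetic study". Cediranib comes first, on an empty stomach, and then: "One hour later, the patient may have a light meal, followed by the morning dose of olaparib".
- **Appendix B, PK expansion diary.** Olaparib is to be taken following a light meal, with no restriction by cycle. The form has columns for both drugs over 28 days.

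**The concern.** A within-patient comparison of a drug alone and in combination is interpretable only if the other determinants of exposure are held constant between the two periods. The protocol treats meals as relevant to dosing both drugs. On the plain wording of Sections 5, 5.2.2 and 7.2.3, olaparib is fasted when given alone and fed when given with cediranib. Pairing cannot separate the two changes, because both occur in every patient at the same time. A food effect could then look like a cediranib interaction, or one in the opposite direction could hide a real interaction.

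The affected result is narrow: the olaparib alone-versus-combination contrast in six patients. Cediranib is fasted under every text, so Cohort 1-T PKced does not have this problem. The expansion opens only after the MTD is set, so dose escalation is untouched, and so is the Phase II PFS analysis.

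**Working it through.** **Step 1. What each text implies for cycle 0 of Cohort 1-T PKolap**

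| Text | Cycle 0 (olaparib alone) | Cycle 1 (combination) |
|---|---|---|
| Section 5 PK schedule | not covered | light meal |
| 5.2.2 and 7.2.3 | fasted | fasted, displaced by the Section 5 schedule |
| 8.14 | light meal on a broad reading; permissive, and timed from a cediranib dose these patients do not take in cycle 0 | light meal |
| PK diary | light meal | light meal |

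The PK-specific texts agree for cycle 1. For cycle 0 the texts split. The cross-references do not resolve this: Section 5 sends the reader to 8.14 for the PK evaluation schedule, and 8.14 sends the reader back to the protocol for dosing.

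Three outcomes are possible:

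- (a) Sections 5, 5.2.2 and 7.2.3 are followed: fasted alone, fed in combination.
- (b) The diary or the broad reading of 8.14 is followed: fed in both periods.
- (c) Practice differs, and the cycle 0 condition varies between patients.

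**Step 2. Bias**

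The plan states no power, variability or significance level for this comparison, so there is no figure to reproduce. Let F be the fed-to-fasted exposure ratio for olaparib tablets and k the number of the six patients fasted in cycle 0. Then

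expected combination-to-alone ratio = true interaction ratio × F^(k/6).

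With no true interaction:

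- k = 0: 1.00.
- k = 3: √0.8 = 0.89, or √1.25 = 1.12.
- k = 6: 0.80, or 1.25.

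At k = 6 the bias is F itself, and more patients would not reduce it.

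**Step 3. False-positive rate (illustration)**

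F and the within-patient CV are assumed. The protocol gives a food effect for cediranib (Section 2.2.1) but none for olaparib tablets. The calculation uses n = 6, a paired two-sided t-test on logs at an assumed 0.05, and critical t (5 df) = 2.571.

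SD of the log difference = √(2 ln(1 + CV²)) = 0.280, 0.415 and 0.545 at CV 20%, 30% and 40%.

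For k = 6 the noncentrality is |ln F| / (SD/√6). For F = 0.8 and CV 20% this is 0.223 / 0.114 = 1.95. For k = 3 the rates come from simulation, because only some patients carry the shift.

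| Patients fasted in cycle 0 | F | CV 20% | CV 30% | CV 40% |
|---|---|---|---|---|
| 0 | any | 5% | 5% | 5% |
| 3 | 0.8 or 1.25 | 9.9% | 7.5% | 6.5% |
| 3 | 0.9 | 6.3% | 5.6% | 5.4% |
| 3 | 1.1 | 6.1% | 5.4% | 5.3% |
| 6 | 0.8 or 1.25 | 35.4% | 19.0% | 13.1% |
| 6 | 0.9 | 11.8% | 8.1% | 6.8% |
| 6 | 1.1 | 10.5% | 7.5% | 6.4% |

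**Step 4. Precision with no food problem**

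The 95% CI for the ratio is the estimate multiplied and divided by exp(2.571 × SD/√6) = 1.34, 1.55 and 1.77 at CV 20%, 30% and 40%. Even a clean comparison can detect only large changes.

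**The case against.** The best defence is that the texts written for the PK cohort favour the harmless reading. Section 8.14 speaks of dosing throughout the PK study, and the same paragraph covers the cycle 0 samples. The diary the patient follows has no cycle exception. Specific instructions would ordinarily override the general rules in 5.2.2 and 7.2.3. The limiting phrase in Section 5 may only introduce a two-drug sequence, and it does not say that cycle 0 is fasted. This makes reading (b) plausible but does not establish it: the meal in 8.14 is optional and tied to a cediranib dose that does not exist in that week, and neither fasting rule carries an exception.

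Other points stand as limits:

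- Section 1.3.4 names the profile in combination, which cycle 1 sampling alone can supply. The contrast with single-agent dosing is set out only in 8.14, and Section 14 lists toxicities alone as Phase 1-T secondary endpoints.
- The size is wholly assumed and could be zero.
- Phase 1-T accrues only at DF/HCC and NCI sites, which limits variation in practice.
- Patients are in clinic for dosing on sampling days, and a Pharmacokinetic Data Form accompanies each sample set, so the meal condition may be recoverable. The form's fields are not shown.
- The table of contents lists an olaparib tablet diary that is not in the available text, so no conclusion is drawn from its absence.

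These points limit the consequence. None identifies a text that fixes the cycle 0 condition.

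**Conclusion.** The concern holds. The documents give conflicting food conditions for olaparib in cycle 0, and one literal reading fully confounds food with cediranib in the comparison for which the lead-in week exists. That the texts conflict is certain. Whether the result is biased depends on which text was followed, and the amount depends on an olaparib food effect the documents do not give. Under reading (b) there is no bias. Under reading (a) the ratio is off by the food effect itself, and a difference in olaparib exposure could not be attributed to cediranib. The illustrative false-positive rates in the tables rest on the assumed F, CV and 0.05 level. The diary shown asks only for date, tablet count and time of dose, so it cannot by itself show afterwards which condition applied. This should be corrected, as a matter confined to one six-patient PK contrast.

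**What to change.** State in Section 8.14, and repeat in Section 5, that olaparib in the PK cohorts is taken after the same light meal in cycle 0 and cycle 1, notwithstanding 5.2.2 and 7.2.3. Make the light meal in 8.14 mandatory rather than optional. Record meal times on PK sampling days, in the diary or in the Pharmacokinetic Data Form if that form does not already capture them.

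If the cohort has already been dosed, establish the cycle 0 meal condition for each patient from site records and report the olaparib comparison with that limitation.

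The cost is one sentence in two places, one changed word and one meal-time entry, with no extra patients, visits or blood draws.

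A separate minor point could be tidied in the same amendment: the interval from cediranib to olaparib is 2 hours in the cycle 1 sampling table and 1 hour in the diary.
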